4.1.2 Exclusion Criteria

Patients who meet any of the following criteria will be excluded from study entry:

- Symptomatic or actively progressing CNS metastases

Note: Asymptomatic patients with treated (i.e., local CNS-directed therapy) or untreated CNS lesions are eligible, provided that all of the following criteria are met:

- Measurable disease, per RECIST v1.1, must be present outside the CNS.
- The patient has no history of intracranial hemorrhage or spinal cord hemorrhage from CNS disease.
- Metastases are limited to the cerebellum or the supratentorial region (i.e., no metastases to the midbrain, pons, medulla, or spinal cord).
- The patient has no symptoms caused by CNS disease (i.e., no headache, nausea, vomiting, convulsion, paralysis, etc.).
- The patient has no ongoing requirement for anticonvulsants for CNS disease.
- The patient has no ongoing requirement for dexamethasone/corticosteroids for CNS disease (previously untreated patients must also not have any history of requiring or receiving dexamethasone/corticosteroids for CNS disease).
- For patients with previously treated CNS metastases, there is no evidence of interim CNS progression between the completion of CNS-directed therapy and randomization.
- For previously untreated patients, there is no evidence of brain edema related to CNS disease (e.g., vasogenic edema).
- For previously untreated patients, a brain magnetic resonance imaging (MRI) scan with contrast is required at screening and is the preferred modality for all subsequent scheduled follow-up tumor assessments.

Note: Computed tomography (CT) scan with contrast may be acceptable for all subsequent scheduled follow-up tumor assessments if the following criteria are met.

- Both brain MRI and CT scan with contrast must be performed at screening to assess untreated CNS disease.
- The CT scan with contrast can be used to reliably evaluate lesions identified on the screening MRI with contrast.

If CT scan with contrast cannot be used to reliably evaluate lesions identified on the screening MRI with contrast, then MRI scan with contrast must be used at all subsequent scheduled follow-up tumor assessments.

The same modality must be used at every tumor assessment.

- Spinal cord compression not definitively treated with surgery and/or radiation, or previously diagnosed and treated spinal cord compression without evidence that disease has been clinically stable for ≥ 1 week prior to randomization

- Leptomeningeal disease
- Uncontrolled pleural effusion, pericardial effusion, or ascites requiring recurrent drainage procedures (once monthly or more frequently)

Patients with indwelling catheters (e.g., PleurX[®]) are allowed regardless of drainage frequency.
- Uncontrolled or symptomatic hypercalcemia (ionized calcium > 1.5 mmol/L, total serum calcium > 12 mg/dL, or corrected calcium > ULN)
- Known clinically significant liver disease, including active viral, alcoholic, or other hepatitis, cirrhosis, and inherited liver disease, or current alcohol abuse
- Malignancies other than SCLC within 5 years prior to randomization, with the exception of those with a negligible risk of metastasis or death (e.g., expected 5-year OS > 90%) treated with expected curative outcome (such as adequately treated carcinoma in situ of the cervix, basal or squamous-cell skin cancer, localized prostate cancer treated surgically with curative intent, ductal breast carcinoma in situ treated surgically with curative intent)
- Active or history of autoimmune disease or immune deficiency, including, but not limited to myasthenia gravis, myositis, autoimmune hepatitis, systemic lupus erythematosus, rheumatoid arthritis, inflammatory bowel disease, antiphospholipid antibody syndrome, *granulomatosis with polyangiitis*, Sjögren syndrome, Guillain-Barré syndrome, or multiple sclerosis (see [Appendix 12](#) for a more comprehensive list of autoimmune diseases and immune deficiencies), with the following exceptions:

Patients with a history of autoimmune-related hypothyroidism who are on thyroid-replacement hormone therapy are eligible for the study.

Patients with controlled Type 1 diabetes mellitus who are on an insulin regimen are eligible for the study.

Patients with eczema, psoriasis, lichen simplex chronicus, or vitiligo with dermatologic manifestations only (e.g., patients with psoriatic arthritis are excluded) are eligible for the study provided all of the following conditions are met:

 - Rash must cover < 10% of body surface area.
 - Disease is well controlled at baseline and requires only low-potency topical corticosteroids.
 - No occurrence of acute exacerbations of the underlying condition requiring psoralen plus ultraviolet A radiation, methotrexate, retinoids, biologic agents, oral calcineurin inhibitors, or high-potency or oral corticosteroids within the previous 12 months.
- History of idiopathic pulmonary fibrosis, organizing pneumonia (e.g., bronchiolitis obliterans), drug-induced pneumonitis, or idiopathic pneumonitis, or evidence of active pneumonitis on screening chest CT scan

History of radiation pneumonitis in the radiation field (fibrosis) is permitted.

- Known active tuberculosis
- Current treatment with anti-viral therapy for HBV or HCV
- Severe chronic or active infection within 4 weeks prior to initiation of study treatment, including, but not limited to, hospitalization for complications of infection, bacteremia, or severe pneumonia, or any active infection that, in the opinion of the investigator, could impact patient safety
- Treatment with therapeutic oral or IV antibiotics within 2 weeks prior to initiation of study treatment

Patients receiving prophylactic antibiotics (e.g., to prevent a urinary tract infection or chronic obstructive pulmonary disease [COPD] exacerbation) are eligible for the study.
- Significant cardiovascular disease, such as New York Heart Association cardiac disease (Class II or greater), myocardial infarction, or cerebrovascular accident within 3 months prior to randomization, unstable arrhythmias, or unstable angina

Patients with known coronary artery disease, congestive heart failure not meeting the above criteria, or left ventricular ejection fraction <50% must be on a stable medical regimen that is optimized in the opinion of the treating physician, in consultation with a cardiologist if appropriate.
- Major surgical procedure other than for diagnosis within 28 days prior to randomization or anticipation of need for a major surgical procedure during the course of the study
- Prior allogeneic bone marrow transplantation or solid organ transplant
- Any other diseases, metabolic dysfunction, physical examination finding, or clinical laboratory finding giving reasonable suspicion of a disease or condition that contraindicates the use of an investigational drug or that may affect the interpretation of the results or render the patient at high risk for treatment complications
- Patients with illnesses or conditions that interfere with their capacity to understand, follow, and/or comply with study procedures
- Treatment with any other investigational agent with therapeutic intent within 28 days prior to randomization
- Administration of a live, attenuated vaccine within 4 weeks before randomization or anticipation that such a live attenuated vaccine will be required during the study

Patients must not receive live, attenuated influenza vaccines (e.g., FluMist®) within 4 weeks prior to randomization, during treatment, and for 5 months following the last dose of study treatment
- Prior treatment with CD137 agonists, T-cell co-stimulating, or immune checkpoint blockade therapies, including anti-CTLA-4, anti-TIGIT, anti-PD-1, and anti-PD-L1 therapeutic antibodies

- Treatment with systemic immunostimulatory agents (including, but not limited to, interferon and interleukin 2) within 4 weeks or 5 drug-elimination half-lives (whichever is longer) prior to randomization
- Treatment with systemic immunosuppressive medications (including, but not limited to corticosteroids, cyclophosphamide, azathioprine, methotrexate, thalidomide, and anti-*tumor necrosis factor* [TNF]- α agents) within 1 week prior to randomization or anticipation of need for systemic immunosuppressive medication during study treatment, with the following exceptions:

Patients who received acute, low-dose systemic immunosuppressant medication or a one-time pulse dose of systemic immunosuppressant medication (e.g., 48 hours of corticosteroids for a contrast allergy) are eligible for the study.

Patients who received mineralocorticoids (e.g., fludrocortisone), corticosteroids for COPD or asthma, or low-dose mineralocorticoids for orthostatic hypotension or low-dose mineralocorticoids and corticosteroids for adrenal insufficiency are eligible for the study.

- History of severe allergic anaphylactic reactions to chimeric or humanized antibodies or fusion proteins
- Known hypersensitivity to CHO cell products or to any component of the tiragolumab or atezolizumab formulations
- History of allergic reactions to carboplatin or etoposide
- Pregnancy or breastfeeding, or intention of becoming pregnant during study treatment or within 5 months after the final dose of atezolizumab or within 90 days after the final dose of tiragolumab or for 6 months after the final dose of carboplatin or etoposide

Women of childbearing potential must have a negative serum pregnancy test result within 14 days prior to randomization.

4.2 METHOD OF TREATMENT ASSIGNMENT AND BLINDING

4.2.1 Treatment Assignment

This is a Phase III, randomized, double-blind, placebo-controlled multicenter study. After written informed consent has been obtained and eligibility has been established, the study site will obtain the patient's identification number and treatment assignment from the interactive voice or web-based response system (IxRS).

Patients will be randomized to one of two treatment arms:

- Arm A: tiragolumab + atezolizumab + CE
- Arm B: placebo + atezolizumab + CE

Randomization will occur in a 1:1 ratio through use of a permuted-block randomization method to ensure that an approximately equal number of patients will be enrolled in each treatment arm within the baseline characteristics of the following stratification factors:

- ECOG Performance Status (0 vs. 1)
- LDH (\leq ULN vs. $>$ ULN)

Patients should receive their first dose of study drug on the day of randomization if possible. If this is not possible, the first dose should occur within 5 days after randomization.

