3.4 RATIONALE FOR STUDY DESIGN

3.4.1 Rationale for Tiragolumab Dose and Schedule

3.4.2 Rationale for Control Arm

The current standard of care in the 1L treatment for ES-SCLC is atezolizumab plus CE (NCCN 2019). In this study, patients in the control arm will receive 4 cycles of placebo plus atezolizumab and CE followed by placebo plus atezolizumab until disease progression per RECIST v1.1. During the maintenance phase, PCI is permitted per local standard of care. This control arm treatment is recognized as the recommended standard of care for the 1L treatment of ES-SCLC (see Section 1.2).

3.4.3 Rationale for Evaluation of Patients without Brain Metastases at Baseline (Primary Analysis Set for Statistical Analysis)

The brain is a common site of metastases for ES-SCLC patients with some studies showing as high as 18% of patients having brain metastases at diagnosis, and up to 80% are expected to have brain disease involvement during the first 2 years following diagnosis (Seute et al. 2004; Pacheco and Bunn 2019). In general, benefits from the immunotherapy and chemotherapy combination have been shown in patients with ES-SCLC. However, this benefit may be attenuated in those with brain metastasis at baseline as seen in the IMpower133 trial where this patient subgroup had a hazard ratio (HR) of 1.07 compared to a HR of 0.68 for patients without brain metastases (Horn et al. 2018).

KEYNOTE-604 is another phase 3 trial that suggests that ES-SCLC patients with brain metastasis at diagnosis may achieve less or no overall survival benefit to first-line immunotherapy plus chemotherapy in comparison to those without. In fact, patients with brain metastases had an OS HR of 1.32 versus 0.75 for patients without brain metastases (Rudin et al. 2020). The CASPIAN study initially reported an OS HR of 0.69 in patients with brain metastasis, however, in the updated analysis the HR became 0.79. The OS HR in those without brain metastasis in initial and updated reports was 0.74 and 0.76, respectively (Paz-Ares et al. 2018, 2020).

It is critical to understand the benefit of the study regimen in both of the patient subgroups, thus, the statistical analyses will be implemented in the PAS first, and then subsequently the FAS.

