6.1 DETERMINATION OF SAMPLE SIZE

The primary objective of this study is to enroll approximately █ patients in the PAS in order to characterize the efficacy profile of tiragolumab plus atezolizumab. Assuming a 15% prevalence of presence or history of brain metastases at baseline, approximately 128 patients in total will be randomized in this study.

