6.4 EFFICACY ANALYSES

Unstratified analysis will be considered as primary results given the potential small sample size within each stratum. The stratified analysis will also be provided.

The stratification factors will be the same as the randomization stratification factors used for IxRS (ECOG Performance Status and LDH) and applied to all endpoints where stratification analyses are planned. Stratification factor(s) may be removed from the stratified analyses if there is risk of overstratification. Analyses based on stratification factors recorded on the eCRF will also be provided if considerable discrepancy is observed between IxRS and eCRF records.

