5.4 SECONDARY ENDPOINTS ANALYSES

5.4.1 Key Secondary Endpoints

5.4.1.1 Progression-Free Survival and Overall Survival in the Full Analysis Set

The estimand is defined similarly as for the co-primary endpoints of PFS and OS in Section 5.3.1 with the exception of the following:

Population: Patients with previously untreated extensive-stage small cell lung cancer.

Same analytical approaches for primary analysis of PFS and OS specified in Section 5.3 will be used to analyze PFS and OS on the FAS.

Subgroup analyses of PFS and OS on the FAS will also be provided by the baseline prognostic factor of presence or history of brain metastases.

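### The pooled full-analysis-set hazard ratios for PFS and OS take no account of brain-metastasis status, the one variable that separates that set from the primary analysis set

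*Protocol*

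**What the plan says.** Protocol 4.2.1 describes allocation as follows: "Randomization will occur in a 1:1 ratio through use of a permuted-block randomization method". The aim is that "an approximately equal number of patients will be enrolled in each treatment arm within the baseline characteristics of the following stratification factors", and the two factors listed are ECOG performance status and LDH.

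Protocol 6.4 makes the unstratified analysis the main efficacy result. For the stratified version it states: "The stratification factors will be the same as the randomization stratification factors used for IxRS (ECOG Performance Status and LDH". A factor may be dropped if strata become too thin; there is no provision for adding one. SAP 5.3.4 refers to the same IxRS factors.

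Protocol 6.4.2.1 and SAP 5.4.1.1 apply the PAS methods to PFS and OS in the FAS. SAP 5.4.1.1 then adds FAS subgroup analyses "by the baseline prognostic factor of presence or history of brain metastases".

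Under SAP 4 the FAS is everyone randomized, and the PAS is those with no present or past brain metastases. Protocol 3.4.3 gives the reason for the split: "this benefit may be attenuated in those with brain metastasis at baseline". On numbers, Protocol 6.1 begins "Assuming a 15% prevalence of presence or history of brain metastases at baseline" and concludes that "approximately 128 patients in total will be randomized in this study".

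The body of SAP 5.3.2, the main analytical approach, is not readable in the public version. That is not held against the plan, but the point rests on the readable text.

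**The concern.** Within the PAS, leaving out brain-metastasis status is harmless because every patient has the same value. The FAS differs from the PAS only by the patients who do have brain metastases. The methods were therefore carried across without the one variable that distinguishes the two sets.

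If brain metastases worsen prognosis and one arm receives more of these patients by chance, the pooled FAS hazard ratio moves against that arm and the PAS hazard ratio does not. The study does no formal testing, and SAP 2 puts the emphasis on consistency with the global study, so point estimates are what will be read. A difference between the PAS and FAS estimates could then partly reflect how the brain-metastasis patients fell between arms.

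**Working it through.** **Inputs from the documents.** About 128 randomized 1:1, so 64 per arm; 15% prevalence of brain metastases (Protocol 6.1); accrual of about 13 months (SAP 3.1). The design medians are redacted. The simulations use the medians that Protocol 1.2 cites for atezolizumab plus chemotherapy in the earlier Phase III trial: 12.3 months for OS and 5.2 months for PFS.

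**Assumptions not in the documents.** Prognostic hazard ratio *g* for brain metastases between 1.25 and 2.0; exponential event times; the follow-up lengths stated below.

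**The plan's own figure.** The PAS target is redacted, so 128 can be checked only for consistency. 128 × 0.85 = 108.8, and a PAS of 108 gives 108 / 0.85 = 127.1, rounded up to 128. The expected number with brain metastases is 128 × 0.15 = 19.2, taken as 19.

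**Chance of imbalance.** Treating the factor as uncontrolled by the randomization, the number *k* of the 19 who fall in one arm is hypergeometric (128, 19, 64).

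- Variance of *k* = 64 × (19/128) × (109/128) × (64/127) = 4.08, so the SD is 2.02.
- The between-arm difference is 2*k* − 19, with SD 4.04.
- 12:7 or worse in either direction (difference of 5 or more): 0.320.
- 13:6 or worse (7 or more): 0.134.
- 14:5 or worse (9 or more): 0.045.

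**Size of the shift at a given split.** Approximately exp[log(*g*) × (p_A − p_B)], where p is the proportion with brain metastases in each arm. At 13:6, p_A − p_B = 13/64 − 6/64 = 0.109. For *g* = 1.25, 1.5 and 2.0 the factor is 1.025, 1.045 and 1.079.

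A simulation with a true treatment hazard ratio of 1 (3,000 runs per cell, minimum follow-up 18 months, about 97 deaths or 123 PFS events) agrees:

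| Split | Endpoint | *g* = 1.25 | *g* = 1.5 | *g* = 2.0 |
|---|---|---|---|---|
| 13:6 | OS | 1.026 | 1.045 | 1.074 |
| 13:6 | PFS | 1.023 | 1.038 | 1.064 |
| 14:5 | OS | 1.025 | 1.057 | 1.104 |

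Stratifying the Cox model by brain-metastasis status brought the mean back to 0.99–1.01 in every cell.

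**Average shift over imbalanced trials.** A second simulation (4,000 trials per scenario, treatment hazard ratio 0.75, cutoff 30 months after the first patient) took trials with a difference of 5 or more. The mean shift in log HR was 0.026, 0.041 and 0.064 for *g* = 1.3, 1.5 and 2.0, that is, factors of 1.026, 1.042 and 1.066. Against a standard error of about 0.215 this is 0.026/0.215 = 0.12 to 0.064/0.215 = 0.30 standard errors.

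**Cost in precision.** Averaged over randomizations, the standard error of the log HR went from 0.212–0.215 unadjusted to 0.215–0.217 stratified, about 1%. At a fixed 13:6 split the OS figures were 0.205 to 0.209 (*g* = 1.25) and 0.200 to 0.210 (*g* = 2.0), an increase of 2% to 5%.

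**The case against.** Much of the case on the other side stands.

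- **The subgroup analysis already exists.** SAP 5.4.1.1 plans FAS hazard ratios within each level of brain-metastasis status, and the PAS is the level without them. The wish in Protocol 3.4.3 to understand benefit in both groups is met by those analyses. What is missing is a single pooled, adjusted FAS estimate; a subgroup of about 19 patients is too imprecise to replace it.
- **Imbalance can be recovered.** SAP 5.7.2 summarizes baseline data by arm for both sets, so subtracting arm sizes gives the count. Its list of characteristics is by example and does not name brain metastases.
- **The stakes are low.** FAS PFS and OS are secondary and testing is exploratory. With about 97 deaths the 95% confidence limits sit a factor of exp(1.96 × 0.203) = 1.49 either side of the estimate, far wider than the shift.
- **The prognostic effect is assumed.** Protocol 4.1.2 admits only asymptomatic CNS disease under strict conditions, which may narrow the prognostic gap.

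Three stronger readings are tempting, and none is supported:

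- A reader might take the subgroup hazard ratios in Protocol 3.4.3 (1.07 against 0.68, and 1.32 against 0.75) as the size of the prognostic effect. They are treatment effects within subgroups. They speak to effect modification, which a covariate in a common-HR model does not address.
- A reader might note that the unadjusted and stratified estimates differ by more than 5% in 14%, 22% and 37% of simulated trials (*g* = 1.3, 1.5, 2.0) and credit all of that to imbalance. About 8% of trials show such a difference with no prognostic effect at all.
- A reader might infer that the randomization is defective. Brain-metastasis status is constant in the primary population, so nothing in the documents requires stratifying on it.

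**Conclusion.** The point holds as a limited gap. No readable text provides a pooled FAS hazard ratio for PFS or OS that accounts for brain-metastasis status, although the SAP labels the factor prognostic and the design uses it to define the primary population. If the unreadable part of SAP 5.3.2 already adds the factor for the FAS, the point falls away; Protocol 6.4 and SAP 5.3.4 give no sign that it does.

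The likely effect is modest. A 12:7 or worse split occurs in about a third of randomizations, and the average shift in the OS hazard ratio is then roughly 3% to 6% on the log scale if the prognostic hazard ratio lies between 1.3 and 2.0. That is well within sampling error, and over repeated randomizations it favours neither arm. The co-primary PAS results are untouched. The case for acting is that the remedy is cheap and removes one non-treatment explanation for a difference between the PAS and FAS estimates.

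**What to change.** In SAP 5.4.1.1, add a supportive Cox model for FAS PFS and FAS OS, stratified by ECOG performance status and LDH, with presence or history of brain metastases as a covariate. Do not cross all three factors into eight strata: about 19 patients over four ECOG-by-LDH cells and two arms is 19/8, or about 2.4 per cell, and Protocol 6.4 already warns of overstratification. Report this estimate beside the unstratified FAS hazard ratio, which remains the main FAS result. Name brain-metastasis status in SAP 5.7.2 as a row in the FAS baseline table by arm. Leave the randomization and all PAS analyses as they are.

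The cost is one more model and a standard error about 1% larger on average, somewhat more when the split is lopsided. Protocol 4.5.6 requires head imaging of every patient at screening, so the covariate should be complete. Protocol 4.5.6 also gives the primary-analysis cutoff as 31 August 2023; if treatment codes are already open, the model must be labelled post hoc.

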4.2.2 Blinding

Study site personnel (with the exception of the unblinded pharmacist) and patients will be blinded to treatment assignment during the study. The Sponsor and its agents will also be blinded to treatment assignment, with the exception of individuals who require access to patient treatment assignments to fulfill their job roles during a clinical trial. These roles include the unblinding group responsible, clinical supply chain managers, sample handling staff, operational assay group personnel, IxRS service provider, and iDMC members.

While PK and immunogenicity samples must be collected from patients assigned to the comparator arm (Arm B) to maintain the blinding of treatment assignment, PK and ADA assay results for tiragolumab in these patients are generally not needed for the safe conduct or proper interpretation of the study data. Laboratories responsible for performing tiragolumab PK and ADA assays will be unblinded to patient treatment assignments to identify appropriate samples for analysis. PK samples from patients assigned to the comparator arm will not be analyzed for tiragolumab PK concentration except by request (e.g., to evaluate a possible error in dosing). Baseline (Cycle 1, Day 1 pre-infusion) immunogenicity samples will be analyzed for all patients. Post-baseline immunogenicity samples from patients assigned to the comparator arm will not be analyzed for ADAs to tiragolumab except by request.

If unblinding is necessary for a medical emergency (e.g., in the case of a serious adverse event for which patient management might be affected by knowledge of treatment assignment), the investigator will be able to break the treatment code by contacting the IxRS. The investigator is not required to contact the Medical Monitor prior to breaking the treatment code; however, the treatment code should not be broken except in emergency situations.

If the investigator wishes to know the identity of the study drug for any reason other than a medical emergency, he or she should contact the Medical Monitor directly. Unblinding may be permitted if an investigator is deciding whether a patient should withdraw from the study and initiate subsequent treatment with a proven therapy. However, unblinding

will not be permitted if an investigator is deciding whether a patient should initiate subsequent treatment with an unproven therapy. The investigator should document and provide an explanation for any non-emergency unblinding.

As per health authority reporting requirements, the Sponsor's Drug Safety representative will break the treatment code for all serious, unexpected suspected adverse reactions (see Section 5.7) that are considered by the investigator or Sponsor to be related to tiragolumab/placebo. The patient may continue to receive treatment, and the investigator, patient, and Sponsor personnel, with the exception of the Drug Safety representative and personnel who must have access to patient treatment assignments to fulfill their roles (as defined above), will remain blinded to treatment assignment.

